
### 13.1. SERUM CONCENTRATION DATA

A listing of PK blood sample collection times and derived sampling time deviations, as well as rituximab concentrations will be provided. Serum concentrations of rituximab will be summarized for each treatment by study day and nominal time point using appropriate descriptive statistics such as number of data (n), mean, SD, CV%, minimum, median, and maximum. Concentrations that are below the limit of quantification (BLQ) will be treated as zero for the computation of descriptive statistics and missing concentration values will be omitted for all concentration summaries. End-of-infusion samples that have been taken prior to the sample taken 3 hour after the start of infusion, will be excluded from descriptive statistics but included in PK parameter analysis (using actual time). Samples with significant deviations from the planned time, as determined by the pharmacokineticist, may be excluded from the calculation of descriptive statistics; these will include samples, which are taken outside a window of 312 to 360 hours at the 336-hour nominal sampling time (i.e., predose sample on Day 15).

A subject listing of all concentration-time data for each treatment will be presented. Concentrations excluded from analyses will be flagged in the listings. Unscheduled assessments will be listed but not included in summary statistics. Plots of arithmetic mean concentration-time data ( $\pm$ SD) will be presented for each treatment on linear and semi-logarithmic scales. Individual subject concentration-time data will be graphically presented on linear and semi-logarithmic scales.

Additional graphical presentations of PK data may be added at the discretion of the PK scientist.

### 13.2. PHARMACOKINETIC PARAMETERS

For PK parameter calculations following the first dose, predose samples that are BLQ or missing will be assigned a numerical value of zero. Any anomalous concentration values observed at predose will be identified in the study report and used for the computation of PK parameters. Pharmacokinetic parameters will be computed if the anomalous concentration is not greater than 5% of the observed maximum concentration ( $C_{max}$ ). If the anomalous concentration is greater than 5% of  $C_{max}$ , the PK parameters for the given subject will be calculated and reported in the listing, but excluded from statistical summaries and analyses. For the second dose, a predose sample that is BLQ will be assigned a numerical value of zero. Missing predose samples will be set to missing.

Any other BLQ concentrations will be assigned a value of zero if they precede quantifiable samples in the initial portion of the profile. A BLQ value that occurs between quantifiable data points prior to  $C_{max}$  will be set to missing. Following  $C_{max}$ , BLQ values embedded between 2 quantifiable data points will be treated as missing when calculating PK parameters. If a BLQ value occurs at the end of the collection interval (after the last quantifiable concentration), it will be set to zero. If consecutive BLQ concentrations are followed by quantifiable concentrations in the terminal portion of the concentration curve, these quantified values will be excluded from

---

Document:	\\ieedc-vnasc01\Biosdata\Archigen\SAIT101\YWA21301\Biostatistics\Documentation\SAP		
Author:		Version Number:	V2.0
		Version Date:	13Feb2019

Template No: CS\_TP\_BS016 Revision 4  
Effective Date: 01Apr2016

Reference: CS\_WI\_BS005

the PK analysis by setting them to missing, unless otherwise warranted by the concentration-time profile.

Subjects with partial data will be evaluated on a case-by-case basis to determine if sufficient data are available for reliable estimation of PK parameters.

The following PK parameters will be estimated for SAIT101, MabThera® and Rituxan® by noncompartmental methods using actual elapsed time, where possible.

$AUC_{(0-t)}$	Area under the serum concentration-time curve from time zero (immediately predose on Day 1) to time of last quantifiable concentration ( $\mu\text{g}\cdot\text{h}/\text{mL}$ ), calculated by linear up/log down trapezoidal summation.
$AUC_{(0-\text{inf})}$	Area under the serum concentration-time curve from zero (immediately predose on Day 1) extrapolated to infinite time ( $\mu\text{g}\cdot\text{h}/\text{mL}$ ), calculated by linear up/log down trapezoidal summation and extrapolated to infinity by addition of the last quantifiable concentration divided by the elimination rate constant: $AUC_{(0-\text{last})} + C_{\text{last}}/\lambda_z$ . For presenting data purpose, symbol $AUC_{(0-\text{inf})}$ instead of $AUC_{(0-\infty)}$ will be used in all PK analysis and reporting.
$AUC_{(0-d15)}$	Area under the serum concentration-time curve from zero (immediately predose on Day 1) until Day 15 prior to infusion ( $\mu\text{g}\cdot\text{h}/\text{mL}$ ), calculated by linear up/log down trapezoidal summation.  Actual time/concentration on Day 15 will be used for the calculation of this parameter unless the parameter is derived by interpolation (see below); 

• A window of 312 to 360 hours postdose for the 336-hour (Day 15) time point (which has been selected as a window that would not create an influence of more than <math>\pm 5\%</math> on the AUC) will be used as an acceptance criterion, for calculation using actual time/concentration on Day 15, and for inclusion of this parameter in descriptive and inferential statistics;

• If the 336-hour sample was collected after 360 hours (i.e., outside the defined time window) but prior to the second dose, then a log-linear interpolation will be used to derive the concentration at 336 hours for computation of <math>AUC_{(0-d15)}</math>;

• If the 336-hour sample is missing or was collected before 312 hours, the <math>AUC_{(0-d15)}</math> will be set to missing.

$AUC_{(w2-w24)}$	Area under the serum concentration-time curve from Week 2 (predose) to Week 24 ( $\mu\text{g}\cdot\text{h}/\text{mL}$ ), calculated by linear up/log down trapezoidal summation.
$AUC_{(0-w12)}$	Area under the serum concentration-time curve from zero (predose) to Week 12 ( $\mu\text{g}\cdot\text{h}/\text{mL}$ ), calculated by linear up/log down trapezoidal summation.
$C_{\text{trough}}$	Trough (predose) concentration ( $\mu\text{g}/\text{mL}$ ) prior to second infusion on Day 15, obtained directly from the observed concentration versus time data. 

• If the sample was collected outside of a window of 312 to 360 hours postdose, <math>C_{\text{trough}}</math> will be excluded for descriptive and inferential statistics.

$C_{\text{max,dose1}}$	Maximum serum concentration ( $\mu\text{g}/\text{mL}$ ) over the 1 st dosing interval, obtained directly from the observed concentration versus time data. This parameter will only be reported if the end-of-infusion concentration is available and evaluable.
$C_{\text{max,dose2}}$	Maximum serum concentration ( $\mu\text{g}/\text{mL}$ ) over the 2 nd dosing interval, obtained directly from the observed concentration versus time data. This parameter will only be reported if the end-of-infusion concentration is available and evaluable.

---

Document:	\\ieedc-vnasc01\Biosdata\Archigen\SAIT101\YWA21301\Biostatistics\Documentation\SAP	Version Number:	V2.0
Author:		Version Date:	13Feb2019

Template No: CS\_TP\_BS016 Revision 4  
Effective Date: 01Apr2016

Reference: CS\_WI\_BS005

$t_{\max, \text{dose1}}$	Time of maximum concentration (h) post-infusion over the 1 st dosing interval, obtained directly from the observed concentration versus time data.
$t_{\max, \text{dose2}}$	Time of maximum concentration (h) post-infusion over the 2 nd dosing interval, obtained directly from the observed concentration versus time data.
$\lambda_z$	Apparent terminal rate constant (1/h), determined by linear regression of the terminal points of the log-linear concentration-time curve. Visual assessment will be used to identify the terminal linear phase of the concentration-time profile. A minimum of 3 data points will be used for determination.
$t_{1/2}$	Apparent terminal half-life (h), determined as $\ln 2/\lambda_z$ .
CL	Systemic clearance after intravenous dosing (L/h), calculated as dose (1 st + 2 nd dose) divided by $AUC_{(0-\text{inf})}$ .
$V_D$	Volume of distribution following intravenous dosing (L), calculated as dose (1 st + 2 nd dose) divided by $[\lambda_z \cdot AUC_{(0-\text{inf})}]$

The following PK parameters will be calculated for diagnostic purposes and listed, but will not be summarized.

$t_{1/2}$ , Interval	The time interval (h) of the log-linear regression to determine $\lambda_z$ .
$t_{1/2}$ , N	Number of data points included in the log-linear regression analysis to determine $\lambda_z$ . A minimum of 3 data points will be used for determination.
$R_{sq}$	Goodness-of-fit statistic for calculation of $\lambda_z$ (Regression coefficient).
%AUC ex	Percentage of $AUC_{(0-\text{inf})}$ obtained by extrapolation, calculated as $[(C_{\text{last}}/\lambda_z)/AUC_{(0-\text{inf})} \times 100]$ .

The following criteria will be assessed:

- if  $AUC_{(0-t)}$  is less than 80.0% of  $AUC_{(0-\infty)}$  (i.e. %AUCex>20.0%), the data will be flagged in the listing.
- if predose concentration is greater than 5% of  $C_{\max, \text{dose1}}$  for a subject, the concentration data and parameters for this subject will be flagged in the listing and excluded from summary statistics.

For partial areas from interval time 1 ( $t_1$ ) to time 2 ( $t_2$ ), if  $t_2$  is missing,  $AUC_{(t_1-t_2)}$  will not be calculated.

Pharmacokinetic parameters will be listed and summarized by treatment using descriptive statistics (n, mean, SD, CV%, minimum, median, maximum, geometric mean, and geometric CV%, except that  $t_{\max}$  will be reported with n, minimum, median, and maximum only).

The additional following summaries of PK parameters will be generated:

- By treatment and region (US, EU, Other)
- By treatment and age category (18-60 years and >60 years)
- By treatment and sex
- By treatment and ADA status at baseline.

The PK parameters,  $AUC_{(0-t)}$ ,  $AUC_{(0-\text{inf})}$ ,  $AUC_{(0-d15)}$ ,  $C_{\max, \text{dose2}}$  after the second infusion on Day 15, and  $C_{\text{trough}}$ , before the second infusion on Day 15 will be considered the co-primary PK endpoints. All other PK endpoints will be regarded as secondary.

A statistical comparison of the loge-transformed primary parameters between treatments will be based on an analysis of variance model. No covariates will be included. The difference in least squares means between the

Document: \\ieedc-vnasc01\Biosdata\Archigen\SAIT101\YWA21301\Biostatistics\Documentation\SAP	
Author:	Version Number: V2.0
	Version Date: 13Feb2019

Template No: CS_TP_BS016 Revision 4	Reference: CS_WI_BS005
Effective Date: 01Apr2016	

test (SAIT101) and the reference (MabThera® or Rituxan®) treatments and the associated 90% CI will be calculated. Comparison between the reference treatments will also be performed. Back transformation will provide the ratio of geometric means between treatments and 90% CI for this ratio. Equivalence will be concluded if the 90% CI for the ratio of geometric means of test/reference for primary endpoints are completely contained within the acceptance interval of 0.80 to 1.25. Least-squares geometric means will be also presented for each treatment with corresponding 95% CIs. BLQ values for  $C_{trough}$  will be treated as LOQ/2 for all statistical comparison. Line plots will be generated to visually display all comparisons for all primary parameters.

A sensitivity analysis will be performed for the above comparisons, in which the above comparison will be replicated, with the addition of the following covariates to the statistical model: Age, sex, ADA status at baseline, body weight at baseline.

An exploratory statistical assessment of the impact of baseline ADA status (Positive or Negative) will be completed by adding this fixed effect to the model used in the primary statistical analysis. The ratio of geometric means for ADA positive/ADA negative will be reported with the 90% CI for this ratio.

Scatter plots of individual and geometric mean PK parameters  $AUC_{(0-inf)}$ ,  $AUC_{(0-t)}$ ,  $AUC_{(0-d15)}$ ,  $C_{max,dose2}$  after the second infusion on Day 15 and  $C_{trough}$  before the second infusion on Day 15 versus treatment will be presented. Additional, graphical presentations of PK data may be added at the discretion of the PK scientist, if further illustration of the PK results is deemed appropriate.

Additional impact analyses will be performed to evaluate the impact of site 10703 on the primary analysis, and the statistical significance of any PK differences associated with this site. The first impact analysis will entail repeating the primary analysis above but excluding site 10703. The second impact analysis will entail adding two fixed effects to the primary model: Site1073 (Yes/No), Site10703 x Treatment interaction, and testing both effects at the two-sided 5% significance level. The type 3 p-values will be reported for all effects in this model, but no treatment or site comparison estimates will be made.

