- n Questionnaires must be completed in the study center by the patient or patient's representative (in case patient is unable to read and/or write) based on the patient's verbal answers.
- o Joint assessor(s) will be independent to the rest of the study team.
- p To be performed by the central laboratory. Screening performed to confirm negative serology for HIV, HBV and HCV. Patients with negative HBsAg and positive HBcAb must have a HBV DNA level <20 IU/mL (or 112 copies/mL) by PCR test. These HBV patients must be willing to undergo PCR HBV DNA testing during treatment and may participate following consultation with a hepatitis expert regarding monitoring and use of HBV antiviral therapy, and provided they agree to receive treatment as indicated. An HBV re-test will be performed monthly including Day 1, Weeks 4, 8, 12, 16, 20, 24, 36,52, early EOS or unscheduled visit, if required. Patients who are confirmed positive and those who have active infections will be excluded from the participation in the study.
- q QuantiFERON Gold test is conducted at Screening. If TB is suspected at any time during the study, chest X-ray and/or QuantiFERON Gold test should be performed (Central Laboratory)
- r To determine presence of hypogammaglobulinemia (IgG <600mg/dL), which is an exclusion criterion.
- s On Day 1 and Day 15 (first and second infusions) blood PK and PD (CD19+ B-cell) samples will be collected before and 3 hours after the start of infusion and immediately (within 10 minutes) before and 1 hour after the end of infusion, **at 48 hours after the start of infusion (Days 3 and 17, in case of 2nd infusion at Day 16, the following PK sampling should be on Day 18)**. The PK and PD samples will also be taken (at the same time of the day first infusion started) at Day 8 (Week 1), Days 29 (Week 4), 57 (Week 8), 85 (Week 12), 113 (Week 16), 141 (Week 20), 169 (Week 24). PD sampling will be additionally collected at D 253 (Week 36), and 365 (Week 52, EOS). Window of each sampling is ± 10 minutes of the determined time points of Days 1, 3, 8, 15 and 17 and ± 3 hours at all other time points.

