### **3.6.1 Schedule of Assessments**

The sequence of assessments at each visit will be standardized as follows (at visits as required by the schedule of assessments):

1. At Visit 1 (Screening): Obtaining of informed consent
2. General assessments: Physical examination, Neurological examination, and Vital signs
3. Efficacy assessments: Patient-reported assessments (patient pain VAS, global VAS, and HAQ-DI)
4. Efficacy assessments: Investigator assessments (swollen and tender joint counts, physician's global assessment of disease activity VAS, EULAR, DAS28)
5. Laboratory/Safety assessments
6. PK/PD/immunogenicity assessments, where applicable
7. If applicable, pre-medication and study drug

All assessments will be performed prior to administration of pre-medication, unless otherwise specified.

Patient-reported data (pain VAS, global VAS, HAQ-DI) should be recorded by the patient on the relevant source documents. In special circumstances when the patient has difficulty writing or is unable to read, the study personnel or patient representative can record this data on behalf of the patient and based on responses provided by the patient verbally. The procedure followed must be documented clearly in the patient notes.

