### 3.6.1.2 Study Drug Administration Part A

Prior to Day 1, patients will be discontinued from their current anti-TNF medication, other biologic DMARDs or non-biologic DMARDs, except MTX.

The following must be performed on **Baseline (Day 1, Week 0)**:

Review inclusion and exclusion criteria and confirm patient eligibility. If eligible, the following procedures should be performed:

- Physical examination and vital signs;
- Neurological examination;
- Documentation of concomitant medications;
- Assessment of AEs/SAEs/ADRs;
- Urine pregnancy test for applicable female;
- Randomization to one of the study drugs;
- Contact IXRS.

The following efficacy assessments will be performed:

- Patient's assessment: global VAS and HAQ-DI, including patient's pain VAS;
- Physician's assessment: global VAS;
- Joint assessment. Each of the 66/68 joints will be evaluated for tenderness and swelling.

The following laboratory assessments will be performed:

- Clinical chemistry, hematology, urinalysis and HBV DNA only when negative HBsAg and positive HbcAb at screening;
- CRP, ESR;
- PK and PD sample collection;
- Immunogenicity.

The following must be also performed:

- The first of the two infusions of the study drug, as per IXRS.

The following must be performed on **Day 3 (Week 0)**:

- Physical / Neurological examination;
- Documentation of concomitant medications;
- Assessment of AEs/SAEs/ADRs;
- PK and PD sample collection.

The following must be performed on **Day 8 (Week 1)**:

- Physical / Neurological examination;
- Documentation of concomitant medications;
- Assessment of AEs/SAEs/ADRs;
- PK and PD sample collection;
- Immunogenicity.

The following must be performed on **Day 15 ± 1 day (Week 2)**:

- Physical examination and vital signs;
- Neurological examination;
- Documentation of concomitant medications;
- Assessment of AEs/SAEs/ADRs;
- Urine pregnancy test for applicable female;
- Contact IXRS;
- The second of the two infusions of study drug, as per IXRS;
- Clinical chemistry, hematology, urinalysis
- PK and PD sample collection;

- Immunogenicity.

The following must be performed on **Day 17 ± 1 day (Week 2)**:

- Physical / Neurological examination;
- Documentation of concomitant medications;
- Assessment of AEs/SAEs/ADRs;
- PK and PD sample collection.

The following must be performed on **Day 29 ± 3 days (Week 4)**:

- Physical / Neurological examination;
- Documentation of concomitant medications;
- Assessment of AEs/SAEs/ADRs.

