## 13. Pharmacokinetics Analysis

The PK data collected in Part A and Part B (up through Week 24) will be analyzed according to the treatment administered.

Serum concentrations of rituximab at the time points pre-defined in the study protocol will be measured by a validated method and used for the PK analysis.

Treatment of PK data affected by important protocol deviations and/or events will include the following:

- Randomized study drug not administered or not fully administered, or wrong trial drug administered: In case a dose is not administered or fully administered, any parameters for this subject, if calculated, for this dose and the subsequent dose will not be included in descriptive and/or inferential statistics; the subject will not be part of the PK analysis set per definition. In case of wrong trial drug being administered, patients will be analyzed and included according to the actual treatment they received (rather than the planned treatment), unless there are other additional factors or changes involved that would impact PK.
- Dose is administered outside of the time window provided in protocol (i.e., visit window of  $\pm 1$  day [i.e. 24 hours] for dose on Day 15): Due to the long half-life and extended duration of blood sampling collections, the impact of sampling time deviations on  $AUC_{(0-inf)}$ ,  $AUC_{(0-inf)}$ -related parameters, and  $AUC_{(0-last)}$  would be considered negligible and those parameters will generally not be excluded from descriptive and/or inferential statistics. Similarly,  $C_{max,d2}$  will not be excluded.
- Total duration of infusion not available (i.e., start and/or stop time of infusion missing): Any concentrations or PK parameters based fully or partially on the affected dose will be evaluated at the BDRM.
- Interruption of infusion: Due to the long half-life of the drug, interruptions are expected to have minimal impact on PK parameters that are susceptible to infusion interruptions, as long as the full dose is administered. No parameters will be excluded based on infusion interruptions.
- Pharmacokinetic samples at important phases of the PK disposition curve collected outside the protocol-defined window and/or missing: Important phases include time points around the end-of-infusion, the last sampling time point, and the trough concentration collected prior to dosing on Day 15.

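### The SAP's 312–360 h limits for the Day 15 predose sample carry no minutes of tolerance, so a protocol-compliant Day 14 sample can lose AUC(0-d15) and Ctrough, two of the five co-primary PK endpoints

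*SAP*

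**What the plan says.** **Protocol.** Sections 3.2.2 and 3.6.1.2 and Table 2 place the second infusion on Day 15 with one day allowed either way. Table 2, footnote s, provides for a Day 16 infusion: in that case "the following PK sampling should be on Day 18". Section 3.1 asks for PK samples at the clock time at which the first infusion began. Section 3.1 and footnote s allow 10 minutes either way on Days 1, 3, 8, 15 and 17. Section 3.6.1 adds: "All assessments will be performed prior to administration of pre-medication, unless otherwise specified". The antipyretic and antihistamine are due 30 to 60 minutes before the infusion.

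**SAP.** Section 13 reads the dosing window as plus or minus one "day [i.e. 24 hours] for dose on Day 15". Section 13.2 sets "A window of 312 to 360 hours postdose for the 336-hour (Day 15) time point" as the acceptance criterion for AUC(0-d15), on the ground that it moves the AUC by no more than 5%. The consequences are:

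- Inside the window, the area runs to the actual sampling time.
- "If the 336-hour sample was collected after 360 hours (i.e., outside the defined time window) but prior to the second dose", the 336 h concentration is obtained by log-linear interpolation.
- "If the 336-hour sample is missing or was collected before 312 hours", AUC(0-d15) becomes missing.
- For Ctrough: "If the sample was collected outside of a window of 312 to 360 hours postdose", the value is left out of descriptive and inferential statistics.

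Section 13.1 names the same window among the reasons for dropping a concentration from the summaries. AUC(0-d15) and Ctrough are both co-primary.

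**The concern.** The sample window and the dosing window are both exactly 24 h either side of 336 h, but a predose sample precedes its dose and has its own timing tolerance. A patient can be dosed on a permitted day and sampled within the permitted minutes, and still lose two co-primary endpoints. SAP Section 4.8.1 gives deviations from sampling times as a common example of a non-significant deviation. Here a sample with no deviation at all can be discarded.

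The AUC rule also treats the two sides differently. A late sample is rescued by interpolation and an early one is deleted. Because accepted values run to the actual time, a patient sampled at 359 h gets a larger AUC(0-d15) than one sampled at 361 h, who is brought back to 336 h.

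At stake are 6 of the 15 equivalence tests (two endpoints, three pairwise comparisons), all of which must succeed.

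**Working it through.** **1. The plan's window.** 336 − 24 = 312 h and 336 + 24 = 360 h. The stated limits are reproduced with nothing added.

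**2. Where compliant samples fall.** I count hours from the start of the first infusion. The SAP says only postdose, but starts the AUC immediately before the Day 1 dose.

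| Second-infusion day | Compliant sample time | Result under the SAP |
|---|---|---|
| Day 14, before the clock time | 311 h 50 min to just under 312 h | AUC(0-d15) missing, Ctrough excluded |
| Day 14, at or after it | 312 h to 312 h 10 min | both kept |
| Day 16, up to the clock time | 359 h 50 min to 360 h | both kept |
| Day 16, after it | just over 360 h to 360 h 10 min | AUC(0-d15) interpolated, Ctrough excluded |

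A dose starting at exactly 312 h is inside the SAP's dosing window, but its predose sample is necessarily earlier than 312 h and so outside the sample window.

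**3. Does the cut at 312.00 h have a pharmacokinetic basis?** I used a two-compartment model with a 4.25 h infusion and the ranges in Protocol Section 1.3.1 (CL 221–242 mL/d, Vss 4.28–4.74 L, half-life 19–22 days). The central volume is not given; I assumed 2.5–3.5 L.

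- AUC to 312 h against AUC to 336 h: −3.1 to −4.4%.
- AUC to 360 h against AUC to 336 h: +2.8 to +4.2%.
- Moving the early limit from 312 h to 311 h 50 min: AUC changes by 0.02–0.03%, Ctrough by 0.05–0.07%.
- Moving it to 311 h: AUC changes by 0.14–0.20%, Ctrough by 0.3–0.4%.

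Ten minutes or an hour at the edge is trivial beside the 24 h already accepted. The second line is also the size of the jump at 360 h: just inside, the value is about 3–4% above its 336 h equivalent; just outside, it is the 336 h value.

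**4. Power.** Two one-sided tests at 5%, true ratio 1, limits 0.80–1.25, log-scale SD = √ln(1 + CV²).

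- CV 33%, n = 84: SD = √ln(1.1089) = 0.3215; SE = 0.3215 × √(2/84) = 0.0496; ln 1.25 / SE = 0.2231 / 0.0496 = 4.50. Power per test, by t distribution, is 99.5%.
- CV 37.3%, n = 84: power per test is 98.1%.
- The plan states 98–99% per test and 81% overall. 0.986¹⁵ = 0.81, so its figures agree with each other and lie between these two CVs.

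The share of patients affected is not in the documents. The table reduces n for the two endpoints only, treats the 15 tests as independent, and applies one CV throughout (power at n = 84 to the ninth power, times power at the reduced n to the sixth).

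| n for the two endpoints | Study-wide, CV 33% | Study-wide, CV 37.3% |
|---|---|---|
| 84 | 93.3% | 75.0% |
| 82 | 92.9% | 73.8% |
| 78 | 91.7% | 71.0% |

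If timing errors are symmetric about the clock time, half of Day 14 samples fall below 312 h. Losing 6 of 84 (7%) then needs about 14% of patients to be dosed on Day 14.

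**The case against.** The strongest reply is that very few patients are touched. Compliant Day 14 samples straddle 312 h, so not all are lost. The protocol plans explicitly for Day 16 and for delay, and says nothing on early dosing beyond the one-day allowance. AUC(0-t), AUC(0-inf) and Cmax are unaffected, and the patient stays in the PK set if any primary parameter is estimable. The rule is prespecified and identical across arms, so no bias in a treatment comparison is shown. SAP Section 13 states the Ctrough exclusion only as a general rule, and Section 13.2 allows case-by-case review of partial data. The 5% allowance for AUC was declared, and the modelled shifts lie within it. All of this stands as a limit on size. It does not remove the mismatch: the AUC(0-d15) rule below 312 h is categorical, and so is the Ctrough rule in Section 13.2.

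A reader might infer three stronger things that the documents do not support.

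- **That most Day 14 samples are lost.** A sample taken before pre-medication for an infusion at the Day 1 clock time would fall at about 311 to 311.5 h, but that is 30–60 minutes from the clock time and so outside the 10-minute tolerance. The order in Section 3.6.1 also yields where timing is otherwise specified. This is a reason for a wider early edge, not evidence that most compliant samples fail.
- **That study-wide power drops materially.** That needs a Day 14 share that appears nowhere.
- **That the SAP's 5% claim is false.** A one-compartment decline with a 19–22 day half-life gives −5.6 to −5.8% at 312 h, but it ignores the distribution phase; the two-compartment figures stay below 5%.

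**Conclusion.** The point holds in a limited form. As written, the SAP can discard protocol-compliant data on two co-primary endpoints at the Day 14 edge, and on Ctrough at the Day 16 edge, over minutes that have no pharmacokinetic meaning. The SAP's dosing and sample windows also conflict at exactly 312 h. Separately, AUC(0-d15) does not measure one fixed interval and jumps by about 3–4% at 360 h.

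The window mismatch follows from the documents alone, given that hours run from the start of the first infusion. If they ran from its end, about 4.25 h later, every compliant Day 14 sample would fall below 312 h, so the origin should be stated. The 3–4% rests on the assumed central volume. The number of patients affected is unknown and the power cost is probably small: at n = 78, about 1.7 points at the stated CV of 33% and about 4 points if 37.3% applied to every endpoint. This is a cheap correction worth making, not a threat to the trial's conclusion.

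**What to change.** In SAP Sections 13, 13.1 and 13.2:

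1. Widen the acceptance window for both AUC(0-d15) and Ctrough at least by the protocol's own tolerance, to 311 h 50 min through 360 h 10 min. Alternatively, set the early edge about 1 h lower, near 311 h, to cover sampling before pre-medication. State that hours run from the start of the first infusion.
2. Derive AUC(0-d15) to exactly 336 h for every accepted sample: log-linear interpolation if drawn after 336 h, as the SAP already does beyond 360 h, and log-linear extrapolation from the Day 8 and predose samples if drawn before. Keep the missing rule for samples that are absent or earlier than the new limit.

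The cost is SAP wording and a small change to the derivation. The downside is an extrapolation of at most about 24–25 h for the earliest samples; the extrapolated piece is roughly 3–4% of the area, so a modest error in slope matters little. A much wider window is not advised for Ctrough, which is not corrected for time: the modelled concentration already falls by about 11–17% between 312 and 360 h. The rule should be settled before the blinded PK/PD data review, so that no edge case is decided patient by patient.
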